3.1.4.1. Handling of Asthma Exacerbations During the Treatment Period

[figure not shown]
Patients should be treated with an OCS burst: 40 to 60 mg (or at least double the current dose) of OCS tapered over a 7- to 10-day period to a new maintenance dose of 2.5 mg above the pre-burst dose. It is understood that im or iv corticosteroid may also be administered as part of the treatment of the asthma exacerbation. If a second OCS burst (doubling of current dose) is required, the patient should be maintained on a fixed OCS dose without any tapering attempts for the remainder of the double-blind treatment phase and the follow-up period.

Patients who complete all scheduled visits will have final procedures and assessments performed at the EOT visit (visit 19). Patients who withdraw from the study before completing the 24-week treatment period will have visit 19 (week 24 \pm 7 days or early termination) procedures and assessments performed at their final visit. Patients will return for a follow-up evaluation 8 weeks (\pm 7 days) after the EOT visit in this study for assessment of pre-bronchodilator spirometry, ACQ-6 score, PK samples, adverse events, blood eosinophils, CAEs and related health care utilizations, and blood for ADA.

The assessments and procedures performed during each study visit are detailed in [Table 5](#) and [Section 3.16](#). If a patient elects to withdraw (or is discontinued from treatment by the investigator), every attempt will be made to continue the assessments subsequent to his/her withdrawal from the study (see [Section 4.5](#)).

The study schema is presented in [Figure 1](#).

Figure 1: Overall Study Schema

Note: An additional, late follow-up for immunogenicity and PK testing will be performed 28 weeks (±2 weeks) after the last dose of study drug (ie, approximately week 48).

AE=adverse event; DoR=day of randomization; EOT=end of treatment; [redacted] F/u=follow up; IP=investigational product; OCS=oral corticosteroid; PK=pharmacokinetic; V=visit; wk=week.

3.2. Justification for Study Design

The rationale for the design of the study is summarized in [Table 4](#).

Table 4: Rationale for Protocol

Area	Rationale
Study population	Representative of the OCS dependent asthma population with elevated blood eosinophils
Investigational product dosage regimen and duration of treatment	Sc dose and regimen based on BREATH iv program Study 3081
Choice of comparison drug(s) (placebo, active)	Placebo control is essential to establish efficacy and safety
Number of subjects (including number per treatment group)	Based on historical OCS reduction studies
Treatment blinding (ie, rationale for blinded or open-label design)	Double-blinding and randomized treatment allocation to prevent bias efficacy study
Primary analysis (measure, variable, time point, statistical test)	Reduction OCS dose is the primary objective
Inclusion of ancillary studies: PK, PD, PGx, immunogenicity	PK and target blood eosinophil PD are important to interpretation of efficacy results  Immunogenicity assessments are essential to evaluate the safety and efficacy of reslizumab
Key safety measures	Standard measures consistent with iv reslizumab studies in eosinophilic esophagitis and eosinophilic asthma

iv=intravenous; OCS=oral corticosteroid; PD=pharmacodynamic; PGx=pharmacogenomic; PK=pharmacokinetic; sc=subcutaneous.

3.3. Primary and Secondary Measures and Time Points

A more detailed description of the efficacy measures is provided in Section 6.

3.3.1. Primary Efficacy Measure and Time Points

The primary efficacy variable and endpoint for this study is the categorized percent reduction in the daily OCS during weeks 20 to 24 compared with the dose at the end of the optimization phase. Refer to Section 6.1 for additional details regarding the categorization of the reduction in OCS dose.

3.3.2. Secondary Efficacy Measures and Time Points

The secondary efficacy measures and time points include the following:

- $\geq 50\%$ reduction in OCS dose, while maintaining asthma control, at weeks 20 to 24 relative to OCS dose at DoR/baseline
- Reduction to ≤ 5 mg daily dose at weeks 20 to 24, while maintaining asthma control
- OCS dose at weeks 20 to 24 relative to DoR/baseline
- Less than 5 mg decrement in OCS dose (ie, the minimal and non-responders) at weeks 20 to 24, while maintaining asthma control
- Clinical asthma exacerbation related:
 - Annualized rate of CAEs requiring a burst of systemic corticosteroid (injection, or if oral, at least a doubling from the current OCS dose for at least 3 days); an asthma-specific hospital admission; or an asthma-specific emergency department visit during the treatment period (weeks 0 to 24)
- OCS discontinuations at weeks 20 to 24, while maintaining asthma control

These measures will be evaluated at the time points in [Table 5](#).

3.3.3. Other Prespecified Efficacy Measures and Time Points

The other efficacy measures and time points include the following:

- Time to first CAE
- Other clinic lung functions, including the following:
 - Spirometry, including pre- and post-bronchodilator FEV₁
- Ambulatory lung function including AM and PM PEF based on the PEF meter
- AQLQ + 12
- ACQ-6
- Total reliever bronchodilator inhalation use (number of inhalations per 24 hours: day and night) based on the daily asthma control diary
- Nighttime awakenings due to asthma requiring rescue inhaler based on the daily asthma control diary
- Asthma symptoms based on the daily asthma control diary
- EQ-5D
- SGRQ

These measures will be evaluated at the time points in [Table 5](#).

3.4. Target Biomarker Measures and Time Points

Blood eosinophils will be determined from blood samples collected at the time points indicated in [Table 5](#).

3.5. Immunogenicity Measures and Time Points

[figure not shown]
Serum ADAs will be determined from blood samples collected from each patient at the time points indicated in [Table 5](#).

3.6. Pharmacokinetic Measures and Time Points

Serum reslizumab concentration will be determined from blood samples collected from each patient at the time points indicated in [Table 5](#). A description of the PK measures is provided in Section [8.1](#).

3.7. Exploratory Measures and Time Points

The exploratory measures for this study include the following and will be evaluated at the time points indicated in [Table 5](#).

3.8. Safety Measures and Time Points

The following safety measures will be implemented throughout the study and evaluated at the time points in [Table 5](#):

- Inquiries about adverse events
- Clinical laboratory evaluations of serum chemistry
- Clinical laboratory evaluations of hematology
- Vital signs (pulse, body temperature, respiratory rate, and blood pressure) assessments
- ECGs
- Physical examinations

- Monitoring and evaluation of any signs and/or symptoms of adrenal insufficiency (OCS withdrawal effects)
- Inquiries about concomitant medication usage

A description of the safety measures is provided in Section 6.15.

3.9. Randomization and Blinding

This is a randomized, double-blind, placebo-controlled study. In order to achieve balance between treatment groups with regard to average daily OCS use/requirement and age, randomization will be stratified by optimized, average daily OCS dose of >10 mg or ≤10 mg and age (12 to <18 years of age or ≥18 years of age) at baseline. Within each stratum, patients will be randomly assigned to receive treatment with sc reslizumab at a dosage of 110 mg every 4 weeks or a matching placebo in a 1:1 ratio. This system is used to ensure a balance across treatment groups.

The randomization list and treatment will be assigned to the relevant treatment groups through a qualified contract research organization (CRO), eg, via Interactive Web Response System (IWRS). Generation of the medication list and management of the interactive response technology (IRT) system will be done by a qualified CRO under the oversight of Teva's Clinical Supply Chain.

The sponsor's personnel involved in the study will also be blinded to the study drug identity after the run-in period until the database is locked for analysis and the treatment assignment is revealed, with the exception of the bioanalytical group (Global Bioassays and Technology), who, in order to facilitate PK and ADA sample analysis, will not be blinded. Eosinophils and monocytes will be redacted from the post-baseline differential cell count reports to avoid the possibility of removing the blind.

3.10. Maintenance of Randomization and Blinding

3.10.1. Randomization

Patient randomization codes will be maintained in a restricted access area within Teva Global Biometrics or in a secure manner with the vendor contracted to create the randomization list. At the time of analysis, when treatment codes are needed, the Teva statistician assigned to the study will make a request to unblind and will receive the unblinded codes.

3.10.2. Blinding/Unblinding

In order to complete the data analysis for PK, it may be necessary to assay samples before database lock. If so, the individuals responsible for sample analysis will know which patients received study drug and which patients received placebo. The randomization codes will be provided to personnel responsible for bioanalysis according to a process that will be predefined in the unblinding plan form (GBP_RD_703_FRM_02) according to Teva Standard Operating Procedure (SOP) GBP_RD_703. The form will be signed at the study initiation stage by the responsible Teva statistician, CRO statistician, and randomization code generator. After authorization has been obtained to release the codes, the randomization code generator at the CRO will provide the codes directly to the bioanalysis team; the statisticians (at Teva and the

CRO) will not be unblinded. Personnel responsible for bioanalysis will not have access to clinical safety and efficacy data and will provide concentration data to any other personnel who may require it in a manner that will not identify individual patients (ie, a dummy patient identifier will be linked to an individual patient’s concentration data).

For information about personnel who may be aware of treatment assignments, see Section 3.9. These individuals will not be involved in conduct of any study procedures or assessment of any adverse events, safety, or efficacy data.

In case of a serious adverse event or pregnancy, in which knowledge of the study drug assignment is needed to make treatment decisions, the investigator may unblind the patient’s drug assignment as deemed necessary, mainly in emergency situations. Individual treatment codes, indicating the treatment randomization for each randomly-assigned patient, will be available to the investigator(s) and/or pharmacist(s) at the study center via the IRT, both via telephone and internet. If possible, the sponsor should be notified of the event before breaking of the code. If this is not possible, the sponsor should be notified immediately afterward, and the patient’s drug code assignment should not be revealed. Breaking of the treatment code can always be performed by the site without prior approval by the sponsor.

When a blind is broken, the patient will be withdrawn from the study, and the event will be recorded onto the case report form (CRF). The circumstances leading to the breaking of the code should be fully documented in the investigator’s study files and in the patient’s source documentation. Treatment assignment should not be recorded in any study documents or source document.

In blinded studies, for adverse events that are defined as suspected, unexpected, serious adverse reaction (SUSAR; ie, reasonable possibility; see Section 7.1.4), the Global Patient Safety and Pharmacovigilance department may independently request that the treatment code be revealed (on a case-by-case basis) to comply with regulatory requirements. The report will be provided in an unblinded manner for regulatory submission. If this occurs, blinding will be maintained for other personnel (eg, the investigator, Teva medical monitor, and study personnel) and the patient will not be withdrawn from the study.

In order to maintain the blinding in this study, each patient will receive either one 1.0-mL sc injection containing 110 mg of reslizumab or one 1.0-mL injection containing sterile placebo solution on each dosing day. Both reslizumab and placebo will be provided as clear solutions.

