4.5.1. Discontinuation of Study Treatment

If premature discontinuation of study treatment occurs for any reason, the patient should continue attending remaining study visits while off study treatment. The patient will continue to receive study provided OCS (prednisone) treatment for the remainder of their participation in the study. The patient should not be considered withdrawn from the study due to interruption or discontinuation of study treatment. For this study, it is very important to continue collecting data from all patients whether or not they complete treatment.

If premature discontinuation of study treatment occurs, the patient should return to the clinic as soon as possible for a study treatment discontinuation visit. All evaluations should be performed as specified in the protocol for the early withdrawal visit (see Table 5). The investigator must determine the reason for and the date of discontinuation of study treatment and record this information in both the source documentation and the Study Drug Treatment Completion CRF. The patient's continued participation in the study must be discussed by the investigator and site staff with the patient; the investigator and site staff must also request the patient to continue attending study visits according to the study visit schedule with all assessments completed up to week 24 (visit 19). The OCS dose and safety assessments at week 24 (visit 19) are the priority assessments for patients that prematurely discontinue study treatment. At a minimum, the investigator should make every effort to obtain information regarding serious adverse events, OCS dose, and survival status at week 24. A safety follow-up visit (visit 20) should be conducted 8 weeks after visit 19.

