4.5.2. Complete Withdrawal from Study

If a patient decides to completely withdraw from the study (ie, refuses any further study participation or contact), all study participation for that patient will cease and all data to be collected at subsequent visits will be considered missing. If a patient decides to completely withdraw from the study, every effort should be made to complete and report the observations outlined in Section 4.5.1 (Discontinuation of Study Treatment) before withdrawal. A complete final evaluation at the time of the patient's withdrawal should be made, including an explanation of why the patient is withdrawing from the study. The reason for and date of withdrawal from the study must be recorded in the source documentation and the Double-Blind Treatment Period Completion CRF.

For patients who are lost to follow-up (ie, patients whose status is unclear because they fail to appear for study visits without stating an intention to withdraw), the investigator should make appropriate efforts to re-establish contact with patient; attempts to contact the patient should be documented in the source documents. If contact has not been re-established, efforts should still be made to locate the patient and obtain information regarding serious adverse events, OCS dose, and survival status at the end of the 24-week treatment period. A patient should only be designated as lost to follow-up if the site is unable to establish contact with the patient after 3 documented attempts via 2 different methods (phone, text, e-mail, certified letter, etc).

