7.2. Pregnancy

All pregnancies that occur during the study, or within 5 months after last IP injection, are to be reported immediately to the medical monitor, and the investigator must provide the Teva Global Pharmacovigilance Department with the pregnancy form. The process for reporting a pregnancy is the same as that for reporting a serious adverse event (see Section 7.1.6.3).

Any patient becoming pregnant during the study will be withdrawn. All patients who become pregnant will be monitored to the completion or termination of the pregnancy. If the pregnancy continues to term, the outcome (health of the infant up to 8 weeks of age), including spontaneous or voluntary termination, details of birth, and presence or absence of any birth defect, congenital abnormalities, or maternal and newborn complications, will be reported to the sponsor. Any complication of pregnancy during the study and any complication of pregnancy that the investigator becomes aware of after termination from the study will be reported as an adverse event or serious adverse event, as appropriate.

If the pregnancy does not continue to term, 1 of the following actions will be taken:

- For a spontaneous abortion, report as a serious adverse event.
- For an elective abortion due to developmental anomalies, report as a serious adverse event.

- For an elective abortion **not** due to developmental anomalies, report on the pregnancy form; do not report as an adverse event.

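### Protocol Section 3.10.2 withdraws a patient from the study after a site code break, while Section 4.5.1 asks that anyone who stops study drug for any reason be followed to week 24 and V20

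*Protocol*

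**What the plan says.** Protocol Section 3.10.2 sets out when the investigator may break the code: "In case of a serious adverse event or pregnancy, in which knowledge of the study drug assignment is needed to make treatment decisions". It then gives the consequence: "When a blind is broken, the patient will be withdrawn from the study, and the event will be recorded onto the case report form (CRF". This section also exempts unblinding by pharmacovigilance for a SUSAR, where the site and study team stay blind "and the patient will not be withdrawn from the study".

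Section 4.5.1 deals with stopping study drug: "If premature discontinuation of study treatment occurs for any reason, the patient should continue attending remaining study visits while off study treatment". It adds: "The patient should not be considered withdrawn from the study due to interruption or discontinuation of study treatment". The stated reason is general: "For this study, it is very important to continue collecting data from all patients whether or not they complete treatment". The site must ask the patient to attend through week 24 (V19). OCS dose and safety at that visit are the priority assessments, and V20 follows 8 weeks later.

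Section 4.5 describes complete withdrawal as the end of participation and contact. Section 4.5.2 states the data consequence for a patient who chooses it: "all study participation for that patient will cease and all data to be collected at subsequent visits will be considered missing".

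Pregnancy has its own rule in Section 7.2: "Any patient becoming pregnant during the study will be withdrawn". Section 4.2(e) and Section 7.3.3.3 say the same. Section 3.14, however, treats pregnancy as the one formal rule for discontinuing study drug.

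**The concern.** The protocol takes care to separate stopping study drug from leaving the study, and wants off-drug data from everyone in the first group. Section 3.10.2 cuts across that separation. Take two patients with the same serious reaction who both stop study drug. If the code stays closed, Section 4.5.1 applies and the week 24 OCS dose is sought. If the treating physician needed the code, Section 3.10.2 takes the patient out of the study.

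What is at stake is the off-drug information on these patients: the visits between the event and week 24, the week 24 OCS dose, and later safety data. SAP Section 6.2.3 plans a sensitivity analysis that relies on this kind of retrieved data. A rule that prevents retrieval works against it, and does so in patients selected by a serious event.

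**Working it through.** The main check is a comparison of texts; arithmetic is needed only for size.

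**1. Do both sections apply to one patient?** Withdrawal from the study ends study drug. Section 4.5.1 is triggered when study drug stops for any reason and lists no exception for unblinding. So a patient unblinded by the site for a serious adverse event falls under both sections. One ends participation and the other asks for visits to V19 and V20.

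**2. Does other text restore the visits?**

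| Protocol section | What it keeps | Scheduled visits to week 24? |
|---|---|---|
| 3.1.4.1, 9.5.6.1 | Best-effort continuation of assessments when a patient elects to withdraw or the investigator stops treatment | Not assured; unblinding not mentioned |
| 3.1.4.1 | V19 procedures performed at the final visit | No; the dose recorded is not the week 24 dose |
| 3.16.4 | Final evaluations and, where possible, the follow-up visit | No |
| 4.5 | Monitoring of an adverse event that led to withdrawal | No; that event only |
| 8.3.1 | Unscheduled ADA sample at a serious adverse event, withdrawal event, severe hypersensitivity reaction or exacerbation | No |

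Part of the information survives. The scheduled visits and the week 24 OCS dose do not.

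**3. Which analyses use what is lost?**
- Primary analysis (Protocol 9.5.6.1, SAP 6.2.2): a patient who stops study drug early is in the lowest category with or without later data. No change.
- Off-drug sensitivity analysis (SAP 6.2.3, Appendix A): uses observed post-discontinuation data and imputes where there are none. The patient moves from observed to imputed. Appendix A's class ET2 describes patients who chose not to remain, which fits a patient removed by rule poorly.
- Tipping-point analysis (SAP Appendix B): the shift is applied to reslizumab patients who stopped early with incomplete follow-up. A withdrawn reslizumab patient joins that group.
- Safety (SAP 3.2, 7.1, 7.3): default summaries for early discontinuers close 4 weeks after the last dose, so the loss is mainly in the separate post-treatment summary.
- Per-protocol set (SAP Table 5): unblinded patients are already excluded. Withdrawal is not needed to protect it.

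**4. Size.** The documents give no expected number of code breaks.
- Assumed range of 1 to 5 patients: 1/152 = 0.7%; 5/152 = 3.3%.
- Rough guide from Protocol 1.3.2.2, with serious adverse events in 6% on reslizumab and 9% on placebo: 76 × 0.06 + 76 × 0.09 = 4.6 + 6.8 = 11.4 patients. If 10% to 30% of these were unblinded by the site (assumed), 1.1 to 3.4 patients. The rates come from intravenous 3 mg/kg studies of up to 52 weeks, so this gives an order of magnitude only.

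**5. Background check on the plan's power figure.** Whitehead's proportional-odds formula is n per arm = 6(z₀.₉₇₅ + z₀.₉₀)² / [ln(OR)² × (1 − Σp̄ᵢ³)].
- Placebo: 10.9, 7.9, 14.8, 10.8 and 55.6%.
- Reslizumab at OR 2.63: 24.3, 13.5, 19.3, 10.6 and 32.3%.
- Result: 74.7, so 75 per arm for 90% power; 76 per arm gives 90.5% (simulated Wilcoxon test 90.1%, 20,000 runs).

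The planned 90% is reproduced. By step 3, code breaks do not alter it through this route.

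**The case against.** The strongest reply is that there is no strict contradiction. Section 4.5.1 says patients are not withdrawn because treatment stopped, whereas Section 3.10.2 withdraws them because the code was broken. Section 4.5.2's missing-data consequence is also written for a patient who refuses further contact, not for one removed by rule. Both readings are fair, so it is an inference that the later data would be missing. But Section 4.5.1 covers stopping for any reason, and nothing tells a site which visits apply after a rule-based withdrawal. The conflict in practice stands.

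A second reply is that assessments at an unblinded site are open to bias, including the OCS dose, which is partly at the investigator's discretion. That is true and calls for a flag. It does not call for discarding the data, since the ITT set keeps all randomized patients.

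Some stronger inferences do not hold:
- A reader might take the SUSAR exemption to show that unblinding is no bar to follow-up. In that case the site stays blind, so the comparison shows nothing about an unblinded site.
- A reader might attribute the loss in pregnancy to Section 3.10.2. Sections 4.2(e), 7.2 and 7.3.3.3 withdraw pregnant patients whether or not the code is broken, and Section 7.2 follows the pregnancy to its outcome.
- A reader might count the week 48 ADA sample among what Section 4.5.1 secures. That section stops at V20 and never mentions V21. It also says that patients should continue and that the site must ask; it does not compel attendance.

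**Conclusion.** The point holds for site code breaks made for a serious adverse event. Sections 3.10.2 and 4.5.1 direct the site differently, and the softer provisions elsewhere do not restore the scheduled visits to week 24.

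The effect is small: probably a few patients at most, on an assumed code-break count that the documents do not supply. It bears on the off-drug sensitivity analysis, the tipping-point analysis and post-treatment safety data.

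It would be tempting to conclude that the primary result or its power is at risk, or that the loss will differ between arms. The documents support neither. The primary category is the same with or without later data, provided the patient stops study drug under either section, and no code-break information by arm is given. This is a low-cost wording improvement, not a threat to the main conclusion.

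**What to change.** Reconcile Section 3.10.2 with Section 4.5.1 so that a site code break does not by itself end data collection. Patients who agree would continue the assessments that Section 4.5.1 already lists through V19 and V20. The code break would be recorded, and the patient excluded from the per-protocol set as SAP Table 5 provides. Assessments made after the code break should carry a flag.

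Separately, the sponsor must reconcile the pregnancy wording in Sections 3.14, 4.2(e), 7.2 and 7.3.3.3, which differ between discontinuing study drug and withdrawing from the study. Changing Section 3.10.2 alone would not alter what happens to those patients. Whether study drug or study prednisone continues after unblinding or in pregnancy is a clinical matter for the sponsor's physicians and is not judged here; Section 4.5.1 ties study prednisone to continued participation, so the revised text should address it explicitly.

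The cost is a protocol wording change; the visits and case report forms already exist. The downside is that a few later assessments will come from unblinded sites.
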